#### 4. Background and Rationale

In order to eliminate *P. vivax* within proposed timeframes (i.e. by 2030) it is essential to directly target the ‘silent’ hypnozoite reservoir sustaining *P. vivax* transmission. Modelling studies show that population mass-screening and treatment (MSAT) of parasite positive individuals will not have a persistent effect on *P. vivax* transmission even if screening is done by PCR (1). Cohort studies conducted in Thailand and Solomon Islands demonstrate that qPCR at a single timepoint detects only 25-30% of all individuals who subsequently have recurrent *P. vivax* infections in the following 10-12 months.

While MDA including an anti-hypnozoitocidal drug such a primaquine is predicted to be highly effective against *P. vivax*, this is logistically challenging: G6PD testing is required to prevent the potentially severe haemolysis associated with 8-aminoquinoline treatment in G6PD-deficient people and directly observed treatment (DOTs) is needed to assure treatment success. However, between 70 – 90% of people living in low- transmission and pre-elimination settings do not experience any *P. vivax* infections over a 12 months period and are thus highly unlikely to carry hypnozoites and would be exposed to the risks of primaquine treatment, without any of its benefits. In short, whilst MSAT misses up to 75% of all individuals requiring treatment (2), MDA “over-treats” up to 90% of the population.

Effective screening with a *P. vivax* sero-diagnostic test may address this gap. As all non-temperate *P. vivax* strains cause a primary infection followed by a primary relapse within 4 weeks to 9 months, a validated panel of serological exposure markers (SEMs) are expected to identify most individuals that potentially harbour hypnozoites (3). SSAT with our novel antigens is therefore predicted to be superior to routine diagnosis and treatment in preventing recurrent *P. vivax* infections and thus reducing *P. vivax* transmission.

Further to the idea of identifying silent and latent/subpatent infections, this project explores the possibility of the shallow vasculature of human skin sequesters and sustains infectious gametocytes of the plasmodia. Gametocytes are the only stage able to continue living inside the mosquito body to undergo a sexual reproduction. Therefore, anopheline feeding time is a critical phase for survival of

this species. However, a typical anopheline has a proboscis about 300 microns in length, in which its protrudable feeding parts are housed. Its feeding depth would certainly not exceed that reach and would probably be considerably shorter. Gametocytes must be near to the surface of the skin in order to infect anopheline mosquitoes (i.e., survive to reproduce). We know that microscopically sub-patent volunteers very often infect anophelines allowed to feed on their skin while being 5-times less likely to infect anophelines simultaneously allowed to membrane feed on a sample of venous blood (4). Other studies have reported very similar findings (5). Those studies corroborate earlier reports of sexual stage gametocytes in skin vasculature occurring at 3-fold higher numbers relative to peripheral blood (finger stick) (6). We hypothesize that gametocytes observed in finger stick samples of vasculature well below 300 microns (typically about 600 microns) rapidly transit that compartment on their way to longer-term sequestration in the microvasculature of the uppermost dermis, just below the epidermis. That is precisely where they need to be, and a protracted residence in that compartment may explain their virtually dormant metabolic state (7), much like that of latent hypnozoites in hepatic cells (8). Human hosts experiencing exceptional and fleeting states of infection like symptomatic patency may go on to host silent, stable, and durable infections of the shallow skin microvasculature by sexual plasmodia. Moreover, these sexual stage should be distributed in such a way to increase the odds of being taken up by the mosquito, i.e. feet and ankle, where anopheles shows the strong preference (9). There is also possibility they have circadian rhythm (10).

The current standard for the diagnosis of malaria in ill patients or healthy residents of endemic areas perform poorly at parasite counts below 50 per microliter blood (11,12). Nucleic acid-based diagnostic techniques offer relatively much greater sensitivity (i.e., from approx. 1/uL to 1/mL), but these assays cannot be done at point-of-care (a sophisticated laboratory and equipment are required), takes days or weeks to complete, requires highly specialized training, and imposes prohibitive direct costs (13). Malaria research leaders and communities identified and acknowledged the need for a point-of-care diagnostic tool with PCR-like sensitivity as a critical need (14,15). The simple, practical, and inexpensive approach to a bedside diagnosis within an hour would effectively empower mass screening and treatment as a means of interrupting malaria transmission in endemic communities, whereas today that practice is futile due to the weakness of diagnostic technology

and the epidemiological dominance of clinically silent sub-patent parasitemias (5). In search of point-of-care diagnostic test, potential of hemozoin as detection tool will also be explored. Previous studies employing magnetic field to capture hemozoin have demonstrated strong preference for gametocytes and increased sensitivity for detection of *P. vivax* asexual stages (16,17). This project will investigate the performance of a point-of-care diagnostic tool employing magneto-optical detection in ankle/feet area which can provide further evidence for the skin reservoir hypothesis.

Moreover, previous studies have demonstrated a higher rate of hemoglobinopathy in malarious areas due to evolutionary pressure (18). Apart from its controversial benefit against malaria, this trait brings substantial health problem to individuals carrying it. This project will investigate the rate of hemoglobinopathy in schoolchildren.

Lastly, radical cure of *P. vivax* is crucial part to stop malaria transmission, therefore compliance and safety monitoring of currently available hypnozoitocidal PQ is essential (19). This project will contribute evidence towards the development of guidelines for high dose PQ in Primary Health Center to establish its use in national scale. The utilisation of cheap and widely used Sahli's Hb measurement for such purpose will be evaluated as well.

## **5. Objectives and Endpoints**

**5.1. Primary objective:** to determine the efficacy of a Serological Screening and Treatment (SSAT) intervention for the prevention of recurrent *P. vivax* malaria.

### **5.2. Secondary objectives:**

1. To evaluate the performance of a point-of-care (POC) anti-*P. vivax* antibody detection test relative to Luminex (MagPix).
2. To evaluate safety of high dose PQ administration in schoolchildren.
3. To evaluate the accuracy of Sahli's method and Standard G6PD (SD Biosensor Inc., Deogyong-daero, Korea) relative to HemoCue for haemoglobin measurement.

4. To estimate the sensitivity and specificity of a microscopic diagnosis of blood by sample from skin (ankle) relative to standard finger stick microscopic and PCR.
5. To measure duration of gametocyte in the blood samples of the skin of the ankle and finger prick.
6. To estimate the sensitivity and specificity of magneto-optical hemozoin detection by Gazelle® (Hemex Health, USA) relative to standard finger stick microscopic and PCR. To analyse hemoglobinopathies in schoolchildren using HemeChip by Gazelle (Hemex Health, USA)

*Primary endpoint:* the proportional reduction of *P. vivax* incidence by PCR in children serologically screened relative to those receiving routine care during 9 months of active follow-up.

*Secondary endpoints:*

- (I) Difference in the time-to recur of *P. vivax* by PCR in SSAT and control arms.
- (II) Difference in the number of recurrent *P. vivax* by PCR in SSAT vs. control arms.
- (III) Difference in the incidence of recurrent symptomatic *P. vivax* by LMF in SSAT vs control arms.
- (IV) Seroconversion rate before and after intervention in SSAT and control arms.
- (V) Sensitivity and specificity of POC antibody detection test vs. gold standard Luminex assay.
- (VI) Adverse event (AE) and Severe Adverse Event (SAE) of high dose PQ in schoolchildren.
- (VII) Hb level in Sahli's method, Standard G6PD (SD Biosensor Inc., Deogyong-daero, Korea), and Gazelle® (Hemex Health, USA), in comparison with HemoCue (HemoCue AB, Angelholm, Sweden).
- (VIII) Sensitivity and specificity of microscopic examination to detect parasitemia from the shallow skin vasculature of the ankle (light microscopy-skin/LMS) compared to standard microscopic (light microscopy-finger/LMF) and PCR.

- (IX) Mean duration time of gametocyte in LMS and LMF
- (X) Sensitivity and specificity of magneto-optical hemozoin detection (MOD) compared to standard malaria detection and PCR.
- (XI) Sensitivity and specificity of Standard G6PD (SD Biosensor, Inc., Deogyong-daero, Korea Korea) compared to CareStart G6PD RDT (Access Bio. Inc., New Jersey, USA).
- (XII) Hemoglobinopathy rate in schoolchildren

## **6. Methodology**

### **6.1. Study site and Participants**

The study will be conducted at mesoendemic area of Malaka regency (124° 38' 32.17" – 125° 5' 21.38" E and 9° 18' 7.19" – 9° 47'26.68" S), West Timor, Indonesia. Formerly known as part of Belu regency, Malaka regency was established in 2012. At north it is adjacent to Belu regency, at south Timor sea, at east Democratic Republic of Timor Leste, and at west South Central Timor and North Central Timor. This area has 20 Primary Health Center (Puskesmas) and one hospital. Most of these Puskesmas (14) reside in malaria endemic areas. The highest Annual Parasite Incidence (API) were reported from Puskesmas Alkani (21.43), Weoe (4.79), and Tunabesi (4.46) in 2018. Working area of Puskesmas Weoe includes 15,652 residents and 16 elementary schools, in contrast with Puskesmas Alkani which only has 6,111 residents and 4 elementary schools. Therefore, we propose to conduct the study at working area of Puskesmas Weoe.

### **6.2. Schools selection and demographic census**

Before the start of the study, a serological survey will be conducted to select the schools. Blood samples will be collected from 20 randomly selected children from each school in Weoe for serological screening with Luminex. Only schools with sero-prevalence of 30-70% will be eligible for enrollment. Maximal number of selected schools will be 6-7, where 800 children will be individually randomized. Demographic census will be conducted during which name, date of birth/age, gender, village, hamlet, parents/guardian will be recorded (census form). Photograph will be taken from each participants to ensure the correct identification for treatment administration and follow up.

### 6.3. Study design and study overview

The study design is a randomized controlled trial with serological screening and treatment as the intervention. Selected schoolchildren will be allocated into two study arms: (1) serological screening and treatment (SSAT), and (2) routine care as control arm.

At enrolment, in the SSAT arm, individuals found *P. vivax* positive by either serological (Luminex) or Giemsa stained microscopic examination regardless of the symptoms will receive supervised treatment (direct observation) with high dose PQ (daily 1 mg/kg BW) for 7 days ( $P_o=P_v$ ). In the control arm, only symptomatic individuals found *P. vivax* positive by Giemsa stained microscopic examination will receive the same regimen ( $P_o=P_v$ ). In addition, in the treated children of both arms, dihydroartemisinin-piperaquine (DHA-PP) will be given as blood schizontocide according to body weight. All other species (*P. falciparum*, *P. malariae*) found by Giemsa stained microscopic examination will be treated according to national guideline. Serological examination will be performed by Luminex (done at Eijkman, Jakarta) and point-of-care (POC) antibody detection using rapid test on site

Follow up will be performed monthly for 9 months. During this period, 400  $\mu$ L of finger pricked blood samples will be collected from all children in both arms. These samples will be tested for malaria presence by PCR which will be done at EO CRU, Jakarta. However, children with clinical symptoms (body temperature of  $\geq 37.5^\circ\text{C}$  and/or history of fever within 3 days), will be examined by Giemsa stained microscopy on site, and treated if positive (any species) according to national guideline (unsupervised).

At the last follow up, a mass blood survey will be conducted to both arms for *Pv* serological test, LMF, and PCR. Those found positive by LMF for any species will be treated regardless of their symptoms.

### 6.4. Inclusion and exclusion criteria

#### Inclusion:

[figure not shown]
- resident of study area and attending selected elementary school in Grade 1-5
- no evidence of health condition that would interfere with study participation
- assent of child and documented parental informed consent

**Exclusion:**

- G6PD deficiency as determined by SD Biosensor quantitative determination of <70% G6PD activity (male: <4 U/g Hb, female: <6 U/g Hb).
- Haemoglobin < 9 g/dL as determined by HemoCue.

These subjects will be referred to PHC for treatment.

**Figure 1. Study Framework**

Staff of Primary Health Center (PHC) of Weoe will be gathered and explained about the study plan. They will be asked to assist our team in the field activity. Then, head and teachers of selected schools will be gathered and explained about the study plan. Finally, meetings which invite parents/ legal guardians of the selected children will be organized 2-3 weeks prior to the study to obtain informed consent from every child. During these meetings the study will be explained to parents/legal guardian of the schoolchildren. At the end of activity, there will be a discussion session. The explanation is arranged in a seminar form by the trained investigator team with ample time of question and answer session. At the end of discussion, informed consent form will be distributed for each parent. They have 1 week to consider whether they will participate in our study or not. The signed informed consent form will be collected by the class teacher and field team.

Trainings will be given for the personnel of PHC that involved in the study, school teachers and health care volunteers. Explanation will be given in details with standard operating procedure (SOP) provided on their duty of each group to facilitate the process of data and sample collection.

## 6.6. Enrolment

During enrolment, finger pricked blood samples will be collected from all participants. At this activity, body temperature will be recorded using infrared thermometers, body weight will be scaled, history of fever within 3 days and taking antimalarial drugs within last 2 weeks will be recorded. Finger pricked blood samples will be made into malaria blood smear and tested by POC Pv antibody rapid detection. A total of 400  $\mu$ L will be collected into microtainer tube containing EDTA to be sent to field laboratory, and separated for various tests, e.g. serology (Luminex), PCR, Hb, G6PD, and Hemex.

All participants' blood samples will be tested for the presence of antibodies to a validated panel of *P. vivax* antigens (using a gold-standard laboratory test) at the Eijkman Institute for Molecular Biology, Jakarta. Blood samples will be shipped every 2 days, and the result will be reported to the field team within no more than 1 week.

On site, blood slides will be Giemsa stained (see 7.3) and assessed by microscopy with 1000x magnification. Screening for G6PD deficiency will be performed quantitatively by Standard G6PD (SD Biosensor, ROK) with the cut off of 4 U/g Hb (male) or 6 U/g Hb (female) on the same day of blood collection. Hb level will be measured using HemoCue and Hb Sahli. Other substudies (LMS, hemozoin detection, hemoglobinopathy) will also be conducted (see 6.10)

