	
standard finger stick microscopic.
 
 
• In the SSAT arm at enrollment, only children who are Pv seropositive and/or LMF Pv/Po positive receive supervised high-dose primaquine (1mg/kg for 7 days) regardless of their symptoms. All blood slides will be processed and read directly after blood collection. Then treatment will follow if positive. Sero-positive children, on the other hand, will commence treatment after the result is available (approximately 1 week). Symptomatic or asymptomatic LMF positive for Pf/Pm will be treated according to current national guidelines.
 
• In the control arm at enrollment, only children who are symptomatic and LMF Pv/Po positive will receive supervised high-dose primaquine (1mg/kg for 7 days).
 
• In both arms at every other timepoint, symptomatic LMF positive children will receive treatment in accordance with national guidelines (unsupervised).
 
• In both arms at the final timepoint, LMF will be conducted on all children and if positive will be treated according to national guidelines.
 
• As blood schizontocides, DHA-PP for 3 days will be given according to body weight (national guidelines).
 

Inclusion and Exclusion Criteria
	
Inclusion:
 
 
• resident of study area and attending selected elementary school in Grade 1-5
 
• no evidence of health condition that would interfere with study participation
 
• assent of child and documented parental informed consent
 
 
Exclusion:
 
 
• G6PD deficiency as determined by SD Biosensor quantitative determination of <70% G6PD activity (male: <4 U/g Hb, female: <6 U/g Hb).
 
• Haemoglobin < 9 g/dL
 

Analysis plan and sample size calculation
	
The study is designed to show a superiority of SSAT vs. routine care for the prevention of recurrent P. vivax infections. The primary study endpoint will be the proportion of children with recurrent P. vivax by PCR during 9 months of follow-up. Secondary endpoints include time-to-first P. vivax recurrence as well as incidence of symptomatic

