	
P. vivax.
 
SSAT intervention is expected to reduce incidence of P. vivax in comparison to standard care. With the previous prevalence rate of 20%, we will have a power of >90% to detect a significant difference with the sample size of 350 children per group. We will anticipate the exclusion of 15% by recruiting 400 children per group.

Lay Summary
	
This study evaluates an experimental serological diagnostic technique intended to identify people at high risk of having dormant malaria parasites in their liver. The findings will assess the ability of this sero test to identify those carriers.
 
800 children living in eastern Indonesia will be individually randomised to the experimental serologic test or routine care.
 
Children in the serological diagnosis arm will be screened for the presence of antibodies to a previously validated panel of malaria antigens optimized for sensitivity to infection during the prior 9 months. Furthermore, they also will be screened by microscopy. If positive by either test, they will be treated for that malaria infection.
 
Children assigned to routine care will be screened by microscopic examination and treated when they show or have history of symptoms in the last 3 days.
 
After initial screening and treating according to diagnostic technique, all children will be actively followed for 9 months with PCR detection every 4 weeks.
 
During 9 month follow up, all children becoming acutely ill and proven to be positive for malaria by microscopy will be treated, in addition, all asymptomatic children will be treated at the final time point.
 
POC serology test will be performed at baseline and final timepoint on all children in both arms. The results from this POC serology test will not be used to inform diagnosis or treatment in any way at either of the timepoints.
 
None of these blood samples will be collected by venopuncture but instead minimally invasive lancet devices will be used.

Sero-diagnostic test
	
Quantitative measurement of antibody titres to a panel of 8 specially selected P. vivax antigens in study subject plasma samples using a Luminex MAGPIX® bead array system. This testing will be done at the Eijkman Institute in Jakarta. The results will be generated in no

	more than 7 days.
--	-------------------

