**APPENDIX I. RETREATMENT SCHEDULE ON ENROLMENT**

LMF	Antimalarial drugs	Pv Serology	
		Positive	Negative
Pf	3d DHP	7d PQ (1 mg/kgBW)	1d PQ (0.25 mg/kg BW)
Pv	3d DHP + 7d PQ	No further treatment	No further treatment
Pm	3d DHP	7d PQ (1 mg/kgBW)	No further treatment
Po	3d DHP + 7d PQ	No further treatment	No further treatment
Mixed Pf&Pv	3d DHP + 7d PQ	No further treatment	No further treatment
Mixed Pf&Pm	3d DHP	7d PQ (1 mg/kgBW)	1d PQ (0.25 mg/kg BW)
Mixed Pv&Pm	3d DHP + 7d PQ	No further treatment	No further treatment

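### Control children's enrolment Luminex results go to the field team for no stated purpose, and the arm-free treatment table in Appendix I conflicts with the control-arm rules

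*Protocol*

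**What the plan says.** On testing and reporting, section 6.6 states: "All participants' blood samples will be tested for the presence of antibodies to a validated panel of" *P. vivax* antigens at the Jakarta laboratory. The next sentence is "Blood samples will be shipped every 2 days, and the result will be reported to the field team within no more than 1 week". Neither sentence distinguishes the arms.

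On who is treated, the synopsis places serology-triggered treatment inside its SSAT bullet. For controls it says "In the control arm at enrollment, only children who are symptomatic and LMF" *Pv/Po* positive receive high-dose primaquine. Section 6.3 repeats the limit: "In the control arm, only symptomatic individuals found" *P. vivax* positive on the slide get that regimen, with *P. ovale* handled in the same way. Section 6.3 sends the other species found by microscopy to the national guideline.

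Appendix I, titled "RETREATMENT SCHEDULE ON ENROLMENT", has seven rows by slide result and two columns by *Pv* serology. It shows neither study arm nor symptom status. The screening form in Appendix J has columns for serology and microscopy and none for arm.

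For two other tests the protocol does say that results stay out of treatment decisions. The synopsis says of the point-of-care (POC) antibody test: "The results from this POC serology test will not be used to inform diagnosis or treatment in any way". Section 6.10 says the same in substance of ankle-skin microscopy. No such sentence covers the Luminex results of controls.

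**The concern.** The trial compares treatment guided by serology with treatment not so guided. That contrast is kept only if serology has no influence on what control children receive. Luminex is the one result that triggers the intervention, yet it is reported to the field for controls as well. The table that staff would consult at enrolment does not say that it excludes controls.

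Two things are at stake. A seropositive control with *Pf* or *Pm* on the slide could be managed differently depending on which page is followed. In addition, no masking is described and smears in months 1–8 are taken only from children with symptoms. Staff who know that a control child is seropositive might therefore ask about fever, take smears or treat differently. Once disclosed, a result cannot be withdrawn, so this has to be settled before enrolment.

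**Working it through.** The point rests mainly on comparing passages. The arithmetic only gives a sense of scale.

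**1. Is there a use for control Luminex results in the field?** The listed uses are seroconversion (sections 6.7 and 8.3) and the accuracy of the POC test against Luminex (section 8.3). Both are analyses and need no early release. School selection (section 6.2) uses a separate survey of 20 children per school before the trial. No operational use in controls is stated.

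**2. Appendix I against the control-arm rules**

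| Slide result | Appendix I | Control rule (synopsis, section 6.3) | Conflict if applied to controls |
|---|---|---|---|
| *Pv*, *Po*, *Pf&Pv*, *Pv&Pm* (4 rows) | DHA-PP plus 7-day primaquine, whatever the serology; no symptom condition | High-dose primaquine only if symptomatic | Yes: symptom condition absent |
| *Pf*, *Pf&Pm* (2 rows) | Seropositive: 7-day primaquine at 1 mg/kg. Seronegative: single 0.25 mg/kg dose | National guideline; high dose limited to *Pv/Po* | Yes, through serology |
| *Pm* (1 row) | Seropositive: 7-day primaquine at 1 mg/kg. Seronegative: nothing further | As above | Yes, through serology |
| Slide-negative | No row | No treatment | None |

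Serology changes treatment in three of the seven rows. The table gives no direction for seropositive, slide-negative children, who are the main group that SSAT adds.

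**3. How many control results would be disclosed as positive?** Section 6.2 admits schools with 30–70% seroprevalence. If the control arm of 400 falls in that range, the count runs from 400 × 0.30 = 120 to 400 × 0.70 = 280. These are children whose serostatus would be known, not children who would be treated.

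**4. Dilution.** Let *e* be the true proportional reduction and *c* the share of that benefit reaching controls. Control incidence becomes I₀(1 − *ec*) and SSAT incidence stays I₀(1 − *e*), so

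observed reduction = 1 − (1 − *e*)/(1 − *ec*).

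For *e* = 0.50:
- *c* = 0.05: 1 − 0.50/0.975 = 48.7%
- *c* = 0.10: 1 − 0.50/0.95 = 47.4%

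The protocol gives no value for *c*. Through Appendix I alone, *c* would be roughly the share of seropositive controls whose slide shows *Pf*, *Pm* or *Pf&Pm*. That share is not stated.

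**5. Power.** The stated power above 90% with 350 per arm (section 8.2) cannot be reproduced, because the simulated effect size is not in the text and Figure 3 is not shown. As an illustration, assume a 20% control risk and a two-sided 5% test. A 44.3% reduction then gives 90% power with 350 per arm. With *c* = 0.05 power falls to about 87%, and with *c* = 0.10 to about 84%.

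**The case against.** The strongest reply is that the protocol already says how controls are treated. The synopsis and section 6.3 both use the word only, and neither lets serology trigger treatment in controls. Appendix I can be read as an SSAT table: it follows the SSAT sequence of slide first and serology later, and its *Pv/Po* rows require no symptoms, as in SSAT. On that reading the defect is a missing label. The objection stands so far as it shows that the plan does not authorise treating controls on serology. It does not remove the missing label, nor the unrestricted report in section 6.6.

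Four stronger readings are tempting, and the documents do not support them.

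- A reader might infer that the plan allows controls to receive the intervention. The two arm-specific rules forbid it.
- A reader might take the 120–280 seropositive controls as the number exposed to contamination. The direct route reaches only those who also have *Pf*, *Pm* or *Pf&Pm* on the slide.
- A reader might infer that health-centre staff, who treat during follow-up (section 6.7), will know serostatus and act on it. Section 6.6 names the field team. Health-centre staff are asked to assist in the field, but no passage says that they receive serology. Follow-up treatment in months 1–8 requires symptoms and a positive slide in both arms.
- A reader might infer detection bias in the primary endpoint. PCR samples are taken monthly from all children whatever their symptoms, so detection is hardly affected.

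The screening form is also weak evidence: it is a blank template whose serology column does not say which test is meant. The workflow figure in Appendix D is not shown and cannot be checked.

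**Conclusion.** The point holds as a contradiction and an unnecessary disclosure. Control Luminex results reach the field team with no stated purpose, and Appendix I, having no arm, conflicts with the synopsis and section 6.3 in its *Pf*, *Pm* and *Pf&Pm* seropositive cells. Its *Pv/Po* rows also conflict, because they carry no symptom condition.

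The likely effect on the primary comparison is small and toward no effect: about 1 to 3 percentage points off a true 50% reduction, if 5–10% of the benefit leaked to controls. That share is an assumption. Knowledge of serostatus bears more on symptom-triggered smears, the treatment that follows them, and the symptomatic secondary endpoint, although that endpoint has a stated fever criterion. This should be fixed because the remedy is cheap and has to come before enrolment, but the documents do not show a serious threat to the primary result.

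**What to change.** - In section 6.6, have the laboratory release enrolment Luminex results to the field team for SSAT children only. Control samples are still assayed, and their results are held at the laboratory until the month-9 visit is complete.
- Complete the serology column of the screening form for SSAT children only.
- State in Appendix I which arm it covers, and reconcile its rows with the synopsis and section 6.3. Which treatment rule is right is for the investigators to settle; the passages only need to agree.

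The cost is a filtered laboratory report and a wording change, with no extra samples or participants. Concealment will be partial: the POC antibody test is done on site in both arms and can be read by eye, so the person reading it still sees an antibody result.
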